**EVAPORATIVE (AIR) SENSITIVITY ASSESSMENT (LMS)**

Please rate **INTENSITY** of this feeling or sensation.

Mark the scale below with an "X" to indicate the best description of that feeling or sensation. Remember, you can mark anywhere on the line, including between the descriptive words.

Tooth Number				
NO PAIN	DIM	DULL	SHARP	STABBING
				
For site use only:	 mm	 Initials		

	Document Name	Clinical Protocol 204930		
	Type	Version	Document Identifier	Effective Date
	eldo_clinical_doc	6.0; Most-Recent; Effective; CURRENT	090032d580c189ed	12-Sep-2016 05:12:55
	Reason For Issue	Auto Issue		

GlaxoSmithKline

RH01897 Visit _____
--------------------------------------

Site No	0	Screening No	S	Visit Date	Day	Month	Year
					2	0	

**EVAPORATIVE (AIR) SENSITIVITY ASSESSMENT (LMS)**

Please rate **DURATION** of this feeling or sensation.

Mark the scale below with an "X" to indicate the best description of that feeling or sensation. Remember, you can mark anywhere on the line, including between the descriptive words.

Tooth Number					
	NO PAIN	TEMPORARY	QUICK	LINGERING	CHRONIC
					
For site use only:	 mm				 Initials

	Document Name	Clinical Protocol 204930		
	Type	Version	Document Identifier	Effective Date
	eldo_clinical_doc	6.0; Most-Recent; Effective; CURRENT	090032d580c189ed	12-Sep-2016 05:12:55
	Reason For Issue	Auto Issue		

RH01897
Visit _____

Site No	0 1	Screening No	S	Visit Date	Day	Month	Year
						2 0	

**EVAPORATIVE (AIR) SENSITIVITY ASSESSMENT (LMS)**

Please rate how much you are able to **TOLERATE** with this feeling or sensation.

Mark the scale below with an "X" to indicate the best description of that feeling or sensation. Remember, you can mark anywhere on the line, including between the descriptive words.

Tooth Number											

 
 NO PAIN	TOLERABLE	UNCOMFORTABLE	UNNERVING	UNBEARABLE	
 
   	
 
		NO PAIN	TOLERABLE	UNCOMFORTABLE	UNNERVING	UNBEARABLE					
NO PAIN	TOLERABLE	UNCOMFORTABLE	UNNERVING	UNBEARABLE							
											
For site use only:	 nm  Initials										

	Document Name	Clinical Protocol 204930		
	Type	Version	Document Identifier	Effective Date
	eldo_clinical_doc	6.0; Most-Recent; Effective; CURRENT	090032d580c189ed	12-Sep-2016 05:12:55
	Reason For Issue	Auto Issue		

RH01897
Visit 

Site No.  	Screening No. 	Visit Date
		   <small>Day Month Year</small>

**EVAPORATIVE (AIR) SENSITIVITY ASSESSMENT (LMS)**

Please give a rating that **DESCRIBES** the kind of feeling this is.

Mark the scale below with an "X" to indicate the best description of that feeling or sensation. Remember, you can mark anywhere on the line, including between the descriptive words.

Tooth Number											

 
 NO PAIN	TWINGE	ACHE	THROBBING	SHOOTING	
 
   	
 
		NO PAIN	TWINGE	ACHE	THROBBING	SHOOTING					
NO PAIN	TWINGE	ACHE	THROBBING	SHOOTING							
											
For site use only:	 mm  Initials										

 GlaxoSmithKline	Document Name	Clinical Protocol 204930		
	Type	Version	Document Identifier	Effective Date
	eldo_clinical_doc	6.0: Most-Recent; Effective: CURRENT	090032d580c189ed	12-Sep-2016 05:12:55
	Reason For Issue	Auto Issue		

## 12.4. APPENDIX 4 - LMS SUBJECT ASSESSMENT FORM (EXAMPLE)

Screening No. S \_\_\_\_\_

Protocol: 204930

Tooth No:

### Labelled Magnitude Scales

Visit No: \_\_\_\_ Date: \_\_\_\_/\_\_\_\_/\_\_\_\_

Please rate the **INTENSITY/DURATION/TOLERABILITY/DESCRIPTION** of this feeling or sensation.  
 Mark the scales below with an "X" to indicate the best description of that feeling or sensation.  
 Remember, you can mark anywhere on the line, including between the descriptive words.

INTENSITY	DURATION	TOLERABILITY	DESCRIPTION
STABBING SHARP DULL DIM NO PAIN	CHRONIC LINGERING QUICK TEMPORARY NO PAIN	UNBEARABLE UNNERVING UNCOMFORTABLE TOLERABLE NO PAIN	SHOOTING THROBBING ACHE TWINGE NO PAIN
Score:  mm	 mm	 mm	 mm
Final v1.0 16 Oct 15			Scorer initials (site staff): 

**NOT TO SCALE**

Document Name	Clinical Protocol 204930		
Type	Version	Document Identifier	Effective Date
eldo_clinical_doc	6.0; Most-Recent; Effective; CURRENT	090032d580c189ed	12-Sep-2016 05:12:55
Reason For Issue	Auto Issue		

## Glossary

AE	Adverse Event
AM	Ante Meridiem (Morning)
ANCOVA	Analysis of Covariance
CI	Confidence Interval
cm	Centimetre
CRO	Clinical Research Organisation
DH	Dentine hypersensitivity
DHEQ	Dentine Hypersensitivity Evaluation Questionnaire
eCRF	electronic Case Report Form
EAR	Erosion, Abrasion, Recession
g	Grams
GI	Gingival Index
GSKCH	GlaxoSmithKline Consumer Healthcare
ITT	Intention-to-Treat
LMS	Labelled Magnitude Scale
mm	Millimetre
MGI	Modified Gingival Index
OST	Oral Soft Tissue
PP	Per Protocol
ppm	Parts Per Million
SAP	Statistical Analysis Plan
TPI	Turesky Modification of the Quigley-Hein Plaque Index
UK	United Kingdom
VAS	Visual Analogue Scale
w/w	Weight/Weight Ratio

 GlaxoSmithKline	Document Name	SAP 204930.doc		
	Type	Version	Document Identifier	Effective Date
	eldo_clinical_doc	1.0; CURRENT; Most-Recent; Effective	090032d580cb2f1e	10-Nov-2016 09:05:48
	Reason For Issue	Auto Issue		

## 1 Introduction

This document describes the statistical methods and data presentations to be used in the summary and analysis of the final data from Protocol 204930. The statistical analysis plan (SAP) will be finalised and approved prior to database lock. This is a non comparative study.

## 2 Objectives

Primary	
To monitor the impact of long term management of DH over a 24 week period, with twice daily use of a sensitivity toothpaste, on the oral health related quality of life in sensitivity sufferers, as measured by the DHEQ.	Change from baseline in DHEQ endpoints over time.
Exploratory	
To evaluate changes in dentine hypersensitivity over the 24 week treatment period, including the number of sensitive teeth, as measured by Schiff Sensitivity Score to assess examiner performance on this measure.	
Mean Schiff Sensitivity Score for all timepoints.
 
Change from baseline in Schiff sensitivity score (two test teeth) for all timepoints.
 
Change from baseline in Schiff sensitivity score (all qualifying teeth) for all timepoints.

To evaluate changes in dentine hypersensitivity over the 24 week treatment period, as measured by Labelled Magnitude Scales (LMS).	At each time point the mean LMS (of each of 4 VAS scales) and change from baseline (for the two test teeth) and will be calculated.

## 3 Study Design

Overall Design
This multi-site, non-comparative design study will be used to monitor the impact of long term management of DH with daily use of a sensitivity toothpaste on the quality of life of a population of sensitivity sufferers. Changes in oral health related quality of life will be monitored using the DHEQ. The study will be conducted in subjects in good general health, with pre-existing self-reported and clinically diagnosed tooth sensitivity at screening.
Visit 1 - Screening Visit

	Document Name	SAP 204930.doc		
	Type	Version	Document Identifier	Effective Date
	eldo_clinical_doc	1.0; CURRENT; Most-Recent; Effective	090032d580cb2f1e	10-Nov-2016 09:05:48
	Reason For Issue	Auto Issue		

The following assessments will be conducted in the order written:

- Written informed consent.
- Review of the oral care products the subject is currently using to confirm they do not contain any ingredients intended for treating sensitive teeth.
- Demographics, concomitant medications and medical history.
- Oral examination including an oral soft tissue (OST) examination and oral hard tissue (OHT) assessments to determine eligible teeth.
- Qualifying evaporative air sensitivity.
- Inclusion/exclusion criteria review.
- Confirmation of subject eligibility.
- Dispensation of acclimatisation toothpaste, toothbrush, diary and timer.
- Supervised brushing with acclimatisation toothpaste.
- Adverse Events (AEs) will be documented from completion of the supervised brushing with acclimatisation toothpaste.

#### Visit 2 - Baseline Visit (Day 0)

The following assessments will be conducted in the order written:

- Review of concomitant medications and AEs.
- Return of acclimatisation toothpaste, toothbrush and diary.
- Review of completed diary to determine usage compliance.
- Inclusion/exclusion criteria review.
- Confirmation of subject eligibility and continuance.
- Completion of DHEQ Section 1 and Section 2.
- LMS Training Exercise
- OST and OHT examinations.
- Evaporative air sensitivity assessment (Schiff Sensitivity Scale, LMS) on all eligible teeth from Visit 1.
- Selection of two test teeth.
- Dispensation of study toothpaste, toothbrush and diary.
- Supervised brushing with study treatment.
- AEs and Incidents from supervised brushing with study treatment

Visit 3 - Week 4 (Day 28 ± 3)

Visit 4 - Week 8 (Day 56 ± 3)

Visit 5 - Week 12 (Day 84 ± 3)

Visit 6 - Week 16 (Day 112 ± 3)

Visit 7 - Week 20 (Day 140 ± 3)

The following assessments will be conducted in the order written:

- Review of concomitant medications, AEs and incidents.
- Return of study toothpaste and diary. New toothbrush at Week 12.
- Review of completed diary to determine usage compliance.

 GlaxoSmithKline	Document Name	SAP 204930.doc		
	Type	Version	Document Identifier	Effective Date
	eldo_clinical_doc	1.0; CURRENT; Most-Recent; Effective	090032d580cb2f1e	10-Nov-2016 09:05:48
	Reason For Issue	Auto Issue		

- Inclusion/exclusion criteria review.
- Confirmation of subject continuance.
- Completion of DHEQ Section 1 (Q7-9) & Section 2.
- OST and OHT examinations.
- Evaporative air sensitivity assessment (Schiff Sensitivity Scale, LMS) on two test teeth.
- Evaporative air sensitivity assessment (Schiff Sensitivity Scale) on remaining eligible teeth from Visit 1.
- Dispensation of study toothpaste and diary (and toothbrush at Visit 5).
- Supervised brushing with study treatment.
- AEs and Incidents from supervised brushing with study treatment

#### Visit 8 – Week 24 (Day 168 ± 3)

The following assessments will be conducted in the order written:

- Review of concomitant medications, AEs and incidents.
- Return of study toothpaste, toothbrush and diary.
- Review of completed diary to determine usage compliance.
- Confirmation of subject continuance.
- Completion of DHEQ Section 1 (Q7-9) & Section 2.
- OST and OHT examination.
- Evaporative air sensitivity assessment (Schiff Sensitivity Scale, LMS) on two selected test teeth.
- Evaporative air sensitivity assessment (Schiff Sensitivity Scale) on remaining eligible teeth from Visit 1.
- AEs and incidents will be recorded for 5 days after last treatment.

The study product is:

- Dentifrice containing 0.454% w/w stannous fluoride (1100ppm fluoride)  
Sensodyne Repair and Protect Daily Repair Toothpaste. German marketplace

## 4 Sample Size Determination

The sample size is based on DHEQ total Score, restrictions, adaptation, social impact, emotional impact and identity, from a previous study [GSKCH Study RH01897].

A sample size of 60 subjects will have at least 90% power to detect significant changes to week 24 for each of the DHEQ variables, with a significance level (alpha) of 0.05 using a two-sided one-sample t-test. No adjustments for multiple testing have been used. Approximately 75 eligible subjects will be allocated the study toothpaste in order to ensure that approximately 60 subjects complete the study. Sixty subjects

 GlaxoSmithKline	Document Name	SAP 204930.doc		
	Type	Version	Document Identifier	Effective Date
	eldo_clinical_doc	1.0; CURRENT; Most-Recent; Effective	090032d580cb2f1e	10-Nov-2016 09:05:48
	Reason For Issue	Auto Issue		

will provide reasonable precision on estimates of DHEQ response and clinical DH assessments.

## 5 Data Considerations

### 5.1 Analysis Populations

The Safety population will consist of all subjects who received the study toothpaste.

The intention to treat (ITT) population will be defined as all subjects who received the study toothpaste and have at least one post- baseline clinical assessment.

The per-protocol (PP) population will be defined as all subjects who received the study toothpaste and have at least one post-baseline clinical assessment and have no protocol violations deemed to affect clinical assessments during the study.

The following will be considered a protocol violation which may warrant exclusion from the PP analysis:

- Violation of inclusion or exclusion criteria that are deemed to affect efficacy.
- Medical history which is deemed to affect efficacy.
- Use of a medication before or during the study, which is felt to affect the assessment of efficacy. The time points affected will be determined prior to database lock.
- Not receiving any study treatment.

The following will be included in the review of protocol violations but will be reviewed on a case-by-case basis to determine whether the data should be excluded from a PP analysis:

- Non compliance with assigned treatment regimen. Treatment compliance will be reviewed on a case-by-case basis prior to database lock to determine the time points from which subject data will be excluded. More details will be given in the Blinded Review Specification Document.
- Assessments outside the time window of the designated time windows Visit 3 - Week 4 (Day 28 ± 3), Visit 4 – Week 8 (Day 56 ± 3), Visit 5 – Week 12 (Day 84 ± 3), Visit 6 – Week 16 (Day 112 ± 3), Visit 7 – Week 20 (Day 140 ± 3) and Week 24 (Day 168 ± 3) will be reviewed on a case-by-case basis prior

 GlaxoSmithKline	Document Name	SAP 204930.doc		
	Type	Version	Document Identifier	Effective Date
	eldo_clinical_doc	1.0; CURRENT; Most-Recent; Effective	090032d580cb2f1e	10-Nov-2016 09:05:48
	Reason For Issue	Auto Issue		

to database lock to determine the time points from which subject data will be excluded. For the analysis, assessments will be assigned to the nominal visit, irrespective of whether the assessment took place within the visit window.

Protocol violations which warrant exclusion from efficacy analysis will be identified between the statistician and Clinical Research Director or designee, before database lock. Further details will be provided in the Data Review Specifications document.

Analysis of all quality of life or hypersensitivity endpoints will be performed on the ITT population. Analysis on the PP population will also be performed if there is more than 10% difference in the number of subjects for the ITT and PP populations.

## 5.2 Subgroups/Stratification

No subgroup or stratified analyses are planned.

## 5.3 Criteria for Evaluation

DHEQ measures captured in the study will be used evaluate changes in oral health related in quality of life over time. OST abnormalities, incidents and AEs reported in the study will be used for safety evaluations of the study treatments.

### 5.3.1 Criteria for Assessing Efficacy

There are no formal success criteria in this study however it is expected that statistically significant changes from baseline will be observed for the DHEQ measures, in particular the Total score.

### 5.3.2 Criteria for Assessing Tolerability

Safety will be assessed with respect to AEs, Incidents and OST abnormalities (oral tolerability).

## 6 Demographics and Baseline Characteristics

### 6.1 Subject Disposition

The subject disposition summary will include the number of screened subjects and screen failures overall. The number and percentage of subjects, in the Safety, ITT and PP populations will be presented. The percentages will be based upon the total number of subjects in the Safety population.

 GlaxoSmithKline	Document Name	SAP 204930.doc		
	Type	Version	Document Identifier	Effective Date
	eldo_clinical_doc	1.0; CURRENT; Most-Recent; Effective	090032d580cb2f1e	10-Nov-2016 09:05:48
	Reason For Issue	Auto Issue		

The number and percentage of subjects completing the study and not completing the study, including a breakdown of the reasons for not completing the study, will be presented. The percentages are based upon the total number of subjects in the Safety population.

A separate summary table of protocol violations leading to exclusion from PP analyses will be produced indicating the number and percentage of subjects with each violation. Percentages will be based on the ITT population.

## 6.2 Demographics and Baseline Characteristics

Descriptive statistics (number of subjects, mean, standard deviation, median, minimum and maximum for continuous variables, and frequency and percentage for categorical variables) will be provided for demographic on baseline data on the Safety, ITT and PP populations.

## 7 Treatment Compliance and Concomitant Medications

### 7.1 Treatment Compliance

Diaries will be used throughout the study to a) allow the subject to familiarize themselves with their completion during the acclimatisation phase and b) promote compliance during the treatment phase. Subjects will not be withdrawn from the study due to missed brushings but will be reminded to use the products supplied as per the instructions provided and to complete the diary after each product usage to encourage compliance.

Study site staff will review the diaries at the start of each visit for compliance and any reports of changes/new medications.

To ensure that subjects understand the dose of toothpaste to be used, staff will demonstrate what is meant by a 'full ribbon' (i.e. covering the length of the toothbrush head), and brushing will be supervised at all assessment visits (at the end of the visit procedures).

Subjects will receive a product use diary. This will outline the brushing instructions and will be used to record each brushing occasion during the study. Subjects will be provided with a new diary at screening, baseline, Week 4, Week 8, Week 12, Week 16 and Week 20 which they will return to the site at the subsequent visit. The number of missed or extra brushings will be recorded in the eCRF and may lead to exclusion from the PP population.

	Document Name	SAP 204930.doc		
	Type	Version	Document Identifier	Effective Date
	eldo_clinical_doc	1.0; CURRENT; Most-Recent; Effective	090032d580cb2f1e	10-Nov-2016 09:05:48
	Reason For Issue	Auto Issue		

Subjects will also be asked to bring all tubes of toothpaste to each study visit for a visual compliance check of product usage.

## 7.2 Concomitant Medications

Concomitant medications used during the study will be databased but no formal listing of these data will be produced. These data will be reviewed for potential exclusions from the PP population.

## 7.3 Medical History

For each subject, the medical history will be taken and reviewed by the Investigator or medically qualified designee. Details of any relevant medical or surgical history, including allergies or drug sensitivity, will be recorded. Any concomitant therapy taken in the 30 days prior to the Screening Visit and throughout the study will also be recorded.

# 8 Efficacy Analysis

## 8.1 Primary Analysis

The null hypothesis for the primary analysis will be:

$H_0$ = There is no difference from baseline in DHEQ endpoints over time.

The alternative hypothesis will be:

$H_1$ = There is statistically significance difference from baseline in DHEQ endpoints over time.

The following DHEQ endpoints will be analysed:

- Section 1, questions 7, 8 and 9 as separate questions
- Total Score (34 item total from Section 2 questions 1 to 34)
- Domains:
  1. Restrictions (4 item total from Section 2 questions 1 to 4)
  2. Adaptation (12 item total from Section 2 questions 5 to 16)
  3. Social Impact (5 item total from Section 2 questions 17 to 21)
  4. Emotional Impact (8 item total from Section 2 questions 22 to 29)
  5. Identity (5 item total from Section 2 questions 30 to 34)
- Global Oral Health Rating (response to Section 2 question 35)
- Effect on Life Overall (4 item total from Section 2 questions 36 to 39)

 GlaxoSmithKline	Document Name	SAP 204930.doc		
	Type	Version	Document Identifier	Effective Date
	eldo_clinical_doc	1.0; CURRENT; Most-Recent; Effective	090032d580cb2f1e	10-Nov-2016 09:05:48
	Reason For Issue	Auto Issue		

Above DHEQ endpoints will be analysed using mixed effect ANOVA with Visit and site as fixed effect, subject as random effect. Adjusted Means will be computed for each visit. Using this model, the post baseline visit will be compared to the baseline visit and difference of their effect will be computed along with P-values and 95% confidence interval.

The visit by site interaction will be investigated by including the visit by site interaction term. If the visit by site interaction term is not significant at the 10% level of significance then this term will be removed from the model.

If the visit site interaction term is significant at 10% level of significance then the interaction will be included in the model and all model estimates (Adjusted Means, 95% CIs and P-values) for within and between visits will be reported separately for each site and based on results from visit by site interaction.

Each of the DHEQ endpoints will be summarised by time point (Baseline, Week 4, 8, 12, 16, 20 and 24).

Standard summary measures, 95% CIs and p- values will be presented. A plot of means of raw scores over time (mean  $\pm$  standard errors) will also be presented for all measures.

Due to the exploratory nature of the study no correction of multiple testing will be performed.

Summary statistics (N, Percentage) will be provided for section 1 (Q1-Q6) and section 2 (Q1 - Q39) of DHEQ questionnaire.

The assumption of normality and homogeneity of variance in the ANOVA model will be investigated. Violation of these assumptions may be overcome using suitable transformation or performing a non-parametric test (e.g., the Wilcoxon signed-rank test).

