#### 9.3.2. Primary Analysis

The following DHEQ endpoints will be analysed:

- Section 1, questions 7, 8 and 9 as separate questions
- Total Score (34 item total from Section 2 questions 1 to 34)
- Domains:
  1. Restrictions (4 item total from Section 2 questions 1 to 4)
  2. Adaptation (12 item total from Section 2 questions 5 to 16)
  3. Social Impact (5 item total from Section 2 questions 17 to 21)
  4. Emotional Impact (8 item total from Section 2 questions 22 to 29)
  5. Identity (5 item total from Section 2 questions 30 to 34)
- Global Oral Health Rating (response to Section 2 question 35)

 GlaxoSmithKline	Document Name	Clinical Protocol 204930		
	Type	Version	Document Identifier	Effective Date
	eldo_clinical_doc	6.0; Most-Recent; Effective; CURRENT	090032d580c189ed	12-Sep-2016 05:12:55
	Reason For Issue	Auto Issue		

- Effect on Life Overall (4 item total from Section 2 questions 36 to 39)

**ABOVE DHEQ ENDPOINTS WILL BE ANALYSED USING MIXED EFFECT ANOVA WITH VISIT AND SITE AS FIXED EFFECT, SUBJECT AS RANDOM EFFECT. ADJUSTED MEANS WILL BE COMPUTED FOR EACH VISIT. USING THIS MODEL THE POST BASELINE VISITS WILL BE COMPARED TO THE BASELINE VISIT AND DIFFERENCE OF THEIR EFFECT WILL BE COMPUTED ALONG WITH P-VALUES AND 95% CONFIDENCE INTERVALS.**

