### 9.3.3. Exploratory Analyses

The following exploratory analyses will be conducted.

At each time point the mean Schiff Sensitivity Score (for the two test teeth and all qualifying teeth) and mean LMS scores [each of 4 scales (description, tolerability, description, intensity)] as well as the change from baseline will be calculated.

**THE MEAN SCHIFF SENSITIVITY (TWO TEST TEETH), MEAN SCHIFF SENSITIVITY (ALL QUALIFYING TEETH) AND MEAN LMS SCORE WILL BE ANALYSED USING THE SAME MODEL MENTIONED AT PRIMARY ANALYSIS AND SIMILAR STATISTICS WILL BE PROVIDED.**

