## 8.2 Exploratory Analyses

The following exploratory analyses will be conducted.

At each time point the mean Schiff Sensitivity Score (for the two test teeth and all qualifying teeth) and mean LMS scores [each of 4 scales (description, tolerability, description, intensity)] as well as the change from baseline will be calculated.

 GlaxoSmithKline	Document Name	SAP 204930.doc		
	Type	Version	Document Identifier	Effective Date
	eldo_clinical_doc	1.0; CURRENT; Most-Recent; Effective	090032d580cb2f1e	10-Nov-2016 09:05:48
	Reason For Issue	Auto Issue		

The above each endpoint will be analysed using mixed effect ANOVA with visit and site as fixed effect, subject as random effect. Adjusted Means will be computed for each visit. Using this model, the post baseline visit will be compared to the baseline visit and difference of their effect will be computed along with P-values and 95% confidence interval.

The visit by site interaction will be investigated by including the visit by site interaction term. If the visit by site interaction term is not significant at the 10% level of significance then this term will be removed from the model.

If the visit site interaction term is significant at 10% level of significance then the interaction will be included in the model and all model estimates (Adjusted Means, 95% CIs and P-values) for within and between visits will be reported separately for each site and based on results from visit by site interaction.

Standard summary measures, 95% CIs and p-values will be presented. A plot of means of raw scores over time (mean  $\pm$  standard errors) will also be presented for all measures.

The assumption of normality and homogeneity of variance in the ANOVA model will be investigated. Violation of these assumptions may be overcome using suitable transformation or performing a non-parametric test (e.g., the Wilcoxon signed-rank test).

The percentage of teeth that are sensitive (Schiff sensitivity score  $>0$  of all qualifying teeth from screening (termed 'the qualifying teeth') will be summarised for each timepoint and also plotted over time.

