[1] Baseline only includes those subjects who have a corresponding post-baseline assessment. Baseline = Day 0.

[2] From mixed effect ANOVA model with visit and site as fixed effect, subject as random effect.

[2] Difference is first named week minus second named week such that a positive difference favors the first named week.

CFB= Change From Baseline;

PPD

PPD

Programming note: Same tables will be populated for- 'Week 12', 'Week 16', 'Week 20' and 'Week 24'. Please repeat tables for the Q8 and Q9.

 GlaxoSmithKline	Document Name	SAP 204930.doc		
	Type	Version	Document Identifier	Effective Date
	eldc_clinical_doc	1.0: CURRENT, Most-Recent, Effective	090032d580cb2f1e	10 Nov 2016 09:05:48
	Reason For Issue	Auto Issue		

Protocol: 207238

Program Run Date: DDMMYYYY

Table 9.3.2.1  
 Summary Statistics of Evaporative (Air) Sensitivity (Schiff Sensitivity Score) By Site and Overall  
 Intent to Treat Population

Study Population: Intent to Treat Population (N=XXX)

TWO TEST TEETH	SITE 1 (N=XX)	SITE 2 (N=XX)	OVERALL (N=XX)
BASELINE			
N (NON-MISSING)	XXX	XXX	XXX
MEAN	X.XXX	X.XXX	X.XXX
SD	X.XXX	X.XXX	X.XXX
SE	XX.X	XX.X	XX.X
MEDIAN	XX.X	XX.X	XX.X
MINIMUM	XX.X	XX.X	XX.X
MAXIMUM	XX.X	XX.X	XX.X
WEEK 4			
N (NON-MISSING)	XXX	XXX	XXX
MEAN	X.XXX	X.XXX	X.XXX
SD	X.XXX	X.XXX	X.XXX
SE	XX.X	XX.X	XX.X
MEDIAN	XX.X	XX.X	XX.X
MINIMUM	XX.X	XX.X	XX.X
MAXIMUM	XX.X	XX.X	XX.X
WEEK 8...			
PPD		PPD	

Programmer note: Please repeat same table for all qualifying teeth.

	Document Name	SAP 204930.doc		
	Type	Version	Document Identifier	Effective Date
	eldo_clinical_doc	1.0: CURRENT: Most Recent: Effective	090032d580cb2f1e	10 Nov 2016 09:05:48
	Reason For Issue	Auto Issue		

Protocol: 204930

Program Run Date: DDMMYYYY

Table 9.3.2.2

Summary and Statistical Analysis of Measures of Dentinal Hypersensitivity (Schiff Sensitivity Score) Over Time

Study Population: ITT (N=XX)

TWO TEST TEETH								
	BASELINE	BASELINE [1]	WEEK 4 VALUES	CFB [1]	BASELINE [1]	WEEK 8 VALUES	CFB [1]	
N	XX	XX	XX	XX	XX	XX	XX	XX
MISSING	XX	XX	XX	XX	XX	XX	XX	XX
MEAN	X.XX	X.XX	X.XX	X.XX	X.XX	X.XX	X.XX	X.XX
SD	X.XXX	X.XXX	X.XXX	X.XXX	X.XXX	X.XXX	X.XXX	X.XXX
SE	X.XXX	X.XXX	X.XXX	X.XXX	X.XXX	X.XXX	X.XXX	X.XXX
MEDIAN	X.X	X.X	X.X	X.X	X.X	X.X	X.X	X.X
MINIMUM	XX	XX	XX	XX	XX	XX	XX	XX
MAXIMUM	XX	XX	XX	XX	XX	XX	XX	XX
ADJUSTED MEAN [2]			XX.XX			XX.XX		
95 % CIS [2]			[X.XX, X.XX]			[X.XX, X.XX]		
P-VALUES [2]			0.XXXX			0.XXXX		

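### The random-subject model gives all six DHEQ changes from baseline one pooled standard error, and the plan never checks whether that standard error fits each contrast

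*SAP*

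**What the plan says.** The primary analysis in SAP 8.1 is: "Above DHEQ endpoints will be analysed using mixed effect ANOVA with Visit and site as fixed effect, subject as random effect". From this one model each post-baseline visit is compared with baseline, with a p-value and a 95% confidence interval. Protocol 9.3.2 specifies the same "MIXED EFFECT ANOVA WITH VISIT AND SITE AS FIXED EFFECT, SUBJECT AS RANDOM EFFECT".

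The exploratory endpoints follow suit. Under Protocol 9.3.3 the Schiff and LMS means "WILL BE ANALYSED USING THE SAME MODEL MENTIONED AT PRIMARY ANALYSIS", and SAP 8.2 repeats "analysed using mixed effect ANOVA with visit and site as fixed effect, subject as random effect".

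On assumptions, SAP 8.1 says: "The assumption of normality and homogeneity of variance in the ANOVA model will be investigated". If they fail, a transformation or a non-parametric test such as the Wilcoxon signed-rank may be used.

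In SAP Appendix 3, the shells for Tables 9.3.1.3 and 9.3.2.2 take the adjusted means, intervals and p-values "From mixed effect ANOVA model with visit and site as fixed effect, subject as random effect". The same shells show the SD and SE of change at each visit on matched subjects: "Baseline only includes those subjects who have a corresponding post-baseline assessment".

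The sample size in SAP 4 was set "with a significance level (alpha) of 0.05 using a two-sided one-sample t-test".

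Neither document names a residual covariance structure, a degrees-of-freedom method or robust standard errors.

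**The concern.** A random subject effect alone implies one common correlation between any two visits and one common variance of difference. Sphericity, meaning equal variances for all visit differences, guarantees that the pooled standard error is right for every contrast. Without it, an interval can be too narrow at one visit and too wide at another within the same table.

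This design gives reason for doubt. All six planned contrasts involve the only pre-treatment visit. If subjects respond to different degrees, correlation between baseline and later visits tends to fall below correlation among later visits. For Schiff, test teeth must score at least 2 at baseline on a 0–3 scale, which restricts the spread at baseline but not afterwards.

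The one-sample t-test used for sizing relies on the variance of the change being tested and needs no such assumption. The amendment log says the paired test was replaced in order to account for site. Accounting for site does not require pooling variance over visit pairs.

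At stake is the calibration of the intervals and p-values for the 11 DHEQ measures and, through the shared model, for Schiff and LMS.

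**Working it through.** **Inputs from the documents.** Seven visits (baseline and Weeks 4, 8, 12, 16, 20, 24); 60 completers of about 75 allocated; two-sided alpha 0.05; visit and site fixed, subject random. No SD, effect size or between-visit correlation is given, so every covariance pattern below is an assumption.

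**The plan's own figure.** The stated power of at least 90% cannot be reproduced without an effect size. Solving backwards, n = 60 and 90% power imply a standardised change of 0.425. The allocation figure is consistent with 20% dropout: 60/0.80 = 75. Neither figure bears on this point.

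**Step 1: pairs.** 7 × 6/2 = 21 visit pairs, of which 6 involve baseline and 15 do not.

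**Step 2: the standard error the model uses.** With complete data, Var(contrast) = 2 × MSE/n on 59 × 6 = 354 df. The expected value of 2 × MSE is the mean variance of difference over the 21 pairs; call it A. A REML fit to one simulated data set (n = 60, two sites, AR(1) 0.8, SD 10) confirmed this. All six contrasts had SE 1.1476, equal to the square root of that data set's 21-pair average divided by 60. The contrast-specific SEs ran from 0.822 (Week 4) to 1.601 (Week 24).

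**Step 3: calibration.** With V the contrast's own variance of change, SE ratio = √(A/V) and type I error ≈ 2 × [1 − Φ(1.967 × ratio)].

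Example with baseline–post correlation 0.5, post–post 0.7 and unit variance: baseline pairs have variance 2(1 − 0.5) = 1.0 and the others 2(1 − 0.7) = 0.6. Then A = (6 × 1.0 + 15 × 0.6)/21 = 0.714, the ratio is √0.714 = 0.845, and type I error is 9.6%.

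Example with correlation falling linearly from 0.7 at one visit apart to 0.5 at six apart: variances by lag are 0.60, 0.68, 0.76, 0.84, 0.92 and 1.00. A = (6 × 0.60 + 5 × 0.68 + 4 × 0.76 + 3 × 0.84 + 2 × 0.92 + 1.00)/21 = 0.733. At Week 24 the ratio is √(0.733/1.00) = 0.86, giving 9.2%. At Week 4 it is √(0.733/0.60) = 1.11, giving 3.0%.

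| Assumed pattern | A | V, Wk 4 / Wk 24 | SE ratio, Wk 4 / Wk 24 | Type I %, Wk 4 / Wk 24 |
|---|---|---|---|---|
| Equal correlation 0.6 | 0.800 | 0.800 / 0.800 | 1.00 / 1.00 | 4.9 / 4.9 |
| Random slope, variance 0.1 over 24 weeks* | 0.826 | 0.803 / 0.900 | 1.01 / 0.96 | 4.6 / 6.0 |
| Random slope, variance 0.3* | 0.878 | 0.808 / 1.100 | 1.04 / 0.89 | 4.0 / 7.9 |
| Linear decline 0.7 to 0.6 | 0.667 | 0.600 / 0.800 | 1.05 / 0.91 | 3.8 / 7.3 |
| Linear decline 0.7 to 0.5 | 0.733 | 0.600 / 1.000 | 1.11 / 0.86 | 3.0 / 9.2 |
| Baseline–post 0.5, post–post 0.6 | 0.857 | 1.000 / 1.000 | 0.93 / 0.93 | 6.9 / 6.9 |
| Baseline–post 0.5, post–post 0.7 | 0.714 | 1.000 / 1.000 | 0.85 / 0.85 | 9.6 / 9.6 |
| Baseline–post 0.5, post–post 0.8 | 0.571 | 1.000 / 1.000 | 0.76 / 0.76 | 13.7 / 13.7 |
| AR(1) 0.8 | 0.839 | 0.400 / 1.476 | 1.45 / 0.75 | 0.4 / 13.8 |
| AR(1) 0.9 | 0.472 | 0.200 / 0.937 | 1.54 / 0.71 | 0.3 / 16.3 |
| Baseline SD half of later SD, correlation 0.6 | 0.757 | 0.650 / 0.650 | 1.08 / 1.08 | 3.4 / 3.4 |

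*Intercept variance 0.6, residual variance 0.4.

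**Step 4: simulation.** Runs of 20,000 per pattern (n = 60, complete data) agreed closely. Simulated Week 24 values were 5.2% under equal correlation, 5.9% and 8.0% for the slopes, 7.2% and 9.3% for the linear declines, and 14.0% and 16.7% for AR(1). A paired t-test at each visit gave 4.7–5.4% in every pattern and visit. Interval coverage is 100% minus the type I figure, whatever the true change.

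**The case against.** The strongest reply is that the homogeneity check would catch the serious cases. If it is run on subject-centred residuals grouped by visit, a median-centred Levene test (n = 60, 2,000 runs) rejects in 78% and 96% of runs under AR(1) 0.8 and 0.9. It rejects in 75% and 99.6% with baseline–post correlation 0.5 and post–post 0.7 and 0.8. The Wilcoxon fallback works on individual changes and so avoids the pooled variance, and the shells print the SE of change for anyone to compare.

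This stands only in part. The SAP does not say the check uses residuals of that kind. On raw scores the same test rejects in 0–2% of runs for those patterns, because their variance is equal at every visit. The mild patterns usually pass either way. The remedy is optional; a transformation does not address correlation, and a Wilcoxon test does not supply the model's interval. No rule acts on a mismatch seen in the shells.

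It is also fair that AR(1) 0.8 is extreme, implying a baseline-to-Week-24 correlation of only 0.8⁶ = 0.26, and that nothing in the documents shows which pattern applies. The study is single-arm and exploratory, reporting 11 measures at six visits without multiplicity correction, so a shift of a few points per contrast is modest. These arguments limit the consequence; they do not remove the defect.

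**Conclusion.** The concern holds. The shared standard error and the missing check on difference variances and correlations follow from the text and the algebra. The size of the error does not: it is nil under sphericity, a few points at Week 24 under mild departures, and two to three times the nominal rate under strong ones. Under decaying correlation the early contrasts are conservative; with a smaller baseline spread all of them can be.

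The figures assume 60 complete subjects. The equality with the 21-pair average becomes approximate with dropout. An additive site term does not alter it, and the same pooling applies within site if the visit-by-site interaction is kept. With complete data the estimated changes are unaffected, and SAP 5.3.1 sets no success rule. The issue is therefore the reliability of the reported intervals and p-values. It should be corrected, but it does not undermine the study.

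**What to change.** In SAP 8.1 and 8.2 and Protocol 9.3.2 (9.3.3 follows by reference), keep visit and site as fixed effects, the visit-by-site step and the same contrasts with baseline. Fit by REML with an unstructured within-subject covariance over the seven visits and Kenward-Roger degrees of freedom. With complete data and additive site, each contrast then reduces to the mean paired change with its own variance, which is the basis of the sample-size test.

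Pre-specify one fallback for non-convergence: for example, a simpler structure with robust standard errors, or a site-adjusted analysis of change from baseline at each visit. Amend the model footnote [2] of Tables 9.3.1.3 and 9.3.2.2 to match.

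The cost is a few lines of SAP and code and no new data. The downsides are 7 × 8/2 = 28 covariance parameters with 60–75 subjects, some chance of needing the fallback, and possibly wider intervals at late visits.
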